The study poses slight risk to participants. The research team will contact each participant each day during the 3-day intervention period to check on their well-being and to monitor for adverse events relating to the diet. Possible mild side-effects include headaches, fatigue, difficulty thinking, moodiness, stomach pain and hunger pangs, and changes in bowel function or frequency of urination. For any participant feeling poorly, the research team member will encourage the participant to stay hydrated, and pass along a report immediately to the PI. The PI will be the primary individual responsible for safety monitoring. If necessary, the participant will be encouraged to cease the diet and resume their usual intake. Any significant adverse side effects including syncope (fainting) or dehydration will lead to immediate cessation of the intervention for that participant.

The research team will review cumulative data from patient feedback on a weekly basis to monitor for adverse effects. No outcomes bad enough to warrant termination of the research study are expected. However, it will be on an individual basis that this option will be considered.

PROVISIONS TO PROTECT THE PRIVACY INTERESTS OF PARTICIPANTS:

We will collect no identifying information with the data of interest to this study. All such deidentified data will be stored on a secure, password-protected computer at the Osher Center for Integrative Medicine or the Department of Preventive Medicine. Only the study research assistant and principal investigators will have access to these data. The trained research assistant will explain all study procedures in detail during the informed consent process and answer any of the participants' questions. Participants' names and mailing addresses will be provided to KitchFix or Pressed Vibrance for the purposes of food/drink delivery only. This information will not be stored with any study data.

Encrypted and computerized data of the laboratory measurement will be used. Throughout the conduct of the present study, stringent guidelines will be used to ensure privacy and confidentiality. The methylation data generated from this project will be stored without the original identifying information in the Department of Preventive Medicine at Northwestern University's Feinberg School of Medicine where all data entry and data management will be performed. Double entry with 100% verification will be used to ensure accuracy of the process.

COMPENSATION FOR RESEARCH-RELATED INJURY:

If any participant appears to become ill or get injured as a result of this study, they will be encouraged to seek medical treatment through their doctor or treatment center of choice. They will be told that they should promptly to tell the PI and research team about any illness or injury.

The university will not pay for medical care required because of a bad outcome resulting from Version #:1.4 Version Date: 05/22/2018

participation in this research study. This does not keep a participant from seeking to be paid back for care required because of a bad outcome.

ECONOMIC BURDEN TO PARTICIPANTS:

This study is not expected to present economic burden to participants. The study will assume the full costs of all special diets used. In addition, the study will take place on Northwestern campus and so it should not incur additional transportation cost for Northwestern students.

CONSENT PROCESS:

Individuals who have completed the screener and who are deemed eligible for the study will be contacted for a phone call. During the phone call, specifics of the study will be described to participants. If they are interested in participating in the study, they will be invited for a lab visit, during which a written informed consent document will be provided. Participants will be given time to read the document and a member of the research team will be available to answer any questions they might have. Participants will then be given a private space to decide if they want to participate in the study, and if so, sign on the informed consent.

Hard-copy informed consent will be provided for the participants to sign during their initial lab visit. The research team will keep the signed documents and offer to make a copy for the participants.

Non-English Speaking Participants

Due to staff limitations, only English-speaking participants will be enrolled in this study.

QUALIFICATIONS TO CONDUCT RESEARCH AND RESOURCES AVAILABLE:

The study procedures will be conducted with a trained research assistant experienced and certified in human subjects research and privacy protections (including HIPAA). It will be supervised by the three PIs, who between them have many years of experience conducting human subjects research. With a small total sample size, recruitment via on-campus advertisements should be achievable in the desired timeframe. Assuming 50% of participants are ineligible or withdraw, we will need access to 36 participants. Participants will be recruited from the multitude of education programs across the Evanston Northwestern campus; Northwestern University is a private institution with a total undergraduate enrollment of 8,353.

The research assistant will be responsible for collecting biospecimen and questionnaire data, and conducting daily follow-up phone calls to monitor participant adherence to the diets of interest. Pls will supervise the study conduct and data collection, monitor potential adverse events, and assist with questions as needed. A trained research assistant will conduct the bloodspot collection and physiologic measurements in a private setting at the Northwestern Medicine Osher Center for Integrative Medicine, located at [name], or a mutually determined private space on campus.

The research assistant and PIs will review the approved study protocol together, along with all consent forms, scripts, and other participant materials to ensure agreement.

Participants will be asked to report significant adverse events as soon as possible to study staff, and will be provided with a study phone number for this purpose. Study physicians will be available to study staff by pager if needed to assess possible adverse events and provide clinical input, including calling participants if indicated.

All persons assisting with the research will participate in relevant weekly or biweekly team meetings (in person or virtual) to remain adequately informed about the protocol, the research procedures, and their duties and functions during recruitment, implementation and data analysis.

The study will take place at the Evanston and Chicago campuses of Northwestern University.

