This group will be provided with the following juices, 1 of each per day, which together will constitute the 800-900 calorie daily diet.

Juice Menu (Delivered by Pressed Vibrance)

Name	Calories	Ingredients	Nutrition
Astound, 16oz	140	Spinach, Kale, Romaine, Cucumber, Fennel, Parsley, Celery, Lemon, Apple, Ginger, Turmeric	Sodium: 95mg / 4% Total Carbohydrates: 34g / 11% Sugar: 18g Protein: 4g Vit A: 240% Vit C: 190% Calcium: 20% Iron: 20%
Delightful Greens, 16oz	170	Kale, Spinach, Cucumber, Romaine, Parsley, Celery, Ginger, Lemon	Sodium: 260mg / 11% Total Carbohydrates: 30g / 11% Sugar: 11g Protein: 12g Vit A: 590% Vit C: 420% Calcium: 45% Iron: 50%
Connective, 16oz	120	Aronia Berry, Spinach, Romaine, Cucumber, Parsley, Lemon, Ginger	Sodium: 110mg / 5% Total Carbohydrates: 28g / 9% Sugar: 15g Protein: 5g Vit A: 230% Vit C: 120% Calcium: 15% Iron: 25%
Mindful, 16oz	130	Spinach, Kale, Romaine, Cucumber, Parsley, Celery, Swiss Chard, Lemon, Lime, Ginger, Apple	Sodium: 250mg / 10% Total Carbohydrates: 24g / 8% Sugar: 11g Protein: 8g Vit A: 330% Vit C: 200% Calcium: 20% Iron: 30%
Nourishment, 16oz	120	Aronia Berry, Spinach, Kale, Romaine, Cucumber, Parsley, Celery, Lemon, Turmeric,	Sodium: 150mg / 6% Total Carbohydrates: 23g / 8% Sugar: 8g

		Ginger, Wheatgrass, Broccoli Sprouts, Sunflower Sprouts	Protein: 7g Vit A: 340% Vit C: 230% Calcium: 25% Iron: 30%
Aronia Crunch, 16oz	140	Apple, Celery, Lime, Aronia Berry	Sodium: 40mg / 2% Total Carbohydrates: 36g / 12% Sugar: 22g Protein: 2g Vit A: 10% Vit C: 45% Calcium: 8% Iron: 6%

Group 2: Juice + Ad Hoc Diet

This group will be provided with the same juices as the above, but will also be instructed to supplement their diet as needed with their own food, without any proscribed caloric, liquid vs. solid, or other restrictions.

Group 3: Caloric Restriction

This group will be provided with the meals below to make up their 900 calorie daily diet.

~900 Calorie Plant-Based Daily Meal Plan (Delivered by KitchFix)	Calories
Loaded Cauliflower Mash (No Bacon) + Strawberry Cashew Yogurt + Power Green Veggie Quinoa Bowl	881
Herbed Root Vegetable Side + Spice Roasted Sweet Potato Side + Paleo Blueberry Muffin + Broccolini	879
Paleo Blueberry Muffin + Loaded Cauliflower Mash (No Bacon) + Spice Roasted Sweet Potato Side + Power Green Veggie Quinoa Bowl	889
Strawberry Cashew Yogurt + Herbed Root Vegetable Side + Tomato and Roasted Garlic Soup	862

Name	Calories	Ingredients	Nutrition
	(Calories from fat)		

STU#:00206611		1	

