Herbed Root Vegetable		Parsnip, carrot, turnip,	Total Fat (g): 3.7
Side, 226.8 g	(34)	redskin potato, high-oleic	
		sunflower oil, parsley,	Trans Fat (g): 0
		salt, black pepper	Cholesterol (mg): 0
			Sodium (mg): 224.6
			Total Carbs (g): 45.6
			Fiber (g): 10.3
			Sugars (g): 13.3
			Added Sugar (g): 0
			Sugar Alcohol (g): 0
			Protein (g): 4.6
			Vitamin A: 306.60%
			Vitamin C: 83.80%
			Calcium: 10.30%
			Iron: 10.50%
			Potassium (mg): 1231.6
			Polyunsat Fat (g): 0.4
			Monounsat Fat (g): 2.6
			Vitamin D: 0.00%
			Vitamin E: 16.20%
			Vitamin K: 85.70%
			Thiamin: 16.90%
			Riboflavin: 9.20%
			Niacin: 14.80%
			Vitamin B6: 22.30%
			Folate: 27.80%
			Vitamin B12: 0.00%
			Pantothenic Acid: 12.40%
			Phosphorus: 17.80%
			Magnesium: 17.20%
			Zinc: 8.80%
			Selenium: 4.00%
			Copper: 17.80%
			Manganese: 46.40%
			Wanganose. 40.4070

STU#:00206611	T	T-	
Spice Roasted Sweet	229	Sweet potato, chili	Total Fat (g): 2.2
Potato Side, 226.8 g	(20)	powder, paprika, coconut	
		oil, salt	Trans Fat (g): 0
			Cholesterol (mg): 0
			Sodium (mg): 349.7
			Total Carbs (g): 66.1
			Fiber (g): 10.4
			Sugars (g): 13.7
			Added Sugar (g): 0
			Sugar Alcohol (g): 0
			Protein (g): 5.3
			Vitamin A: 929.90%
			Vitamin C: 13.00%
			Calcium: 10.30%
			Iron: 12.70%
			Potassium (mg): 1126.7
			Polyunsat Fat (g): 0
			Monounsat Fat (g): 0
			Vitamin D: 0.00%
			Vitamin E: 7.60%
			Vitamin K: 9.70%
			Thiamin: 17.10%
			Riboflavin: 12.60%
			Niacin: 10.10%
			Vitamin B6: 35.70%
			Folate: 9.00%
			Vitamin B12: 0.00%
			Pantothenic Acid: 26.10%
			Phosphorus: 15.80%
			Magnesium: 20.90%
			Zinc: 7.00%
			Selenium: 3.30%
			Copper: 25.40%
			Manganese: 43.30%
	1		

\$10#:00206611	1	T	T

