Paleo Blueberry Muffin, 62.0 g	162 (106)	MUFFIN almond flour, coconut flour, banana, almond butter, almonds, baking powder, salt, baking soda, vanilla extract, coconut oil, maple syrup, coconut milk, pastured eggs, cinnamon, blueberries	Total Fat (g): 11.7 Sat. Fat (g): 3.3 Trans Fat (g): 0 Cholesterol (mg): 36.4 Sodium (mg): 87.8 Total Carbs (g): 13.2 Fiber (g): 3.5 Sugars (g): 6.9 Added Sugar (g): 3.4 Sugar Alcohol (g): 0 Protein (g): 4.8 Vitamin A: 1.60% Vitamin C: 3.70% Calcium: 5.40% Iron: 15.90% Potassium (mg): 101.8 Polyunsat Fat (g): 0 Monounsat Fat (g): 0 Vitamin D: 2.00% Vitamin E: 52.20% Vitamin K: 0.10% Thiamin: 0.60% Riboflavin: 1.70% Niacin: 0.80% Vitamin B6: 2.40% Folate: 1.90% Vitamin B12: 1.50% Pantothenic Acid: 0.40% Phosphorus: 3.10% Magnesium: 4.30% Zinc: 1.60% Selenium: 0.20% Copper: 1.40% Manganese: 11.50%

Broccolini, 226.8 g	81	Broccolini, garlic, salt, Total Fat (g): 0.	9
	(8)	black pepper, lemon zest, Sat. Fat (g): 0.1	
	(0)	chili flake Trans Fat (g): 0	
		Cholesterol (mg	
		Sodium (mg): 14	
		Total Carbs (g):	
		Fiber (g): 6.1	
		Sugars (g): 3.9	
		Added Sugar (g	1): 0
		Sugar Alcohol (
		Protein (g): 6.6	3,
		Vitamin A: 29.40	0%
		Vitamin C: 338.9	90%
		Calcium: 11.209	
		Iron: 9.60%	
		Potassium (mg)	: 734.2
		Polyunsat Fat (g	
		Monounsat Fat	(g): 0
		Vitamin D: 0.00	%
		Vitamin E: 9.00	%
		Vitamin K: 289.	10%
		Thiamin: 11.009	%
		Riboflavin: 15.9	0%
		Niacin: 7.40%	
		Vitamin B6: 21.	10%
		Folate: 35.80%	
		Vitamin B12: 0.0	
		Pantothenic Aci	
		Phosphorus: 15	
		Magnesium: 12	.20%
		Zinc: 6.40%	.,
		Selenium: 8.509	%
		Copper: 6.10%	
		Manganese: 27	.90%

STU#:00206611			
Tomato and Roasted	187	SOUP tomato, vegetable	
Garlic Soup, 453.6 g	(57)	broth, onion, red bell	Sat. Fat (g): 1.1
		pepper, garlic, carrot,	Trans Fat (g): 0
		cashew, tomato paste,	Cholesterol (mg): 0
		olive oil, basil, salt, black	Sodium (mg): 278.3
		pepper, chili flakes	Total Carbs (g): 27
		GARNISH basil	Fiber (g): 4.4
			Sugars (g): 13.8
			Added Sugar (g): 0
			Sugar Alcohol (g): 0
			Protein (g): 5.9
			Vitamin A: 114.20%
			Vitamin C: 135.90%
			Calcium: 9.50%
			Iron: 12.00%
			Potassium (mg): 693.6
			Polyunsat Fat (g): 0
			Monounsat Fat (g): 0
			Vitamin D: 0.00%
			Vitamin E: 4.00%
			Vitamin K: 25.50%
			Thiamin: 5.60%
			Riboflavin: 2.50%
			Niacin: 2.30%
			Vitamin B6: 12.20%
			Folate: 4.30%
			Vitamin B12: 0.00%
			Pantothenic Acid: 2.50%
			Phosphorus: 8.70%
			Magnesium: 9.80%
			Zinc: 5.30%
			Selenium: 4.90%
			Copper: 14.10%

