			Manganese: 22.80%
			5

PROCEDURES INVOLVED:

Up to 30 participants (15 males and 15 females) will be enrolled in the study and will be randomized into one of the three arms (we expect each arm will have three male and three female participants after attrition): the "juice fasting" arm, the "juice in addition to normal diet" arm, and the "caloric restriction diet" arm. Participants will come into the lab for an initial visit, during which they will complete questionnaires on their usual diet and demographics and will be informed about their assignment to one of the three arms.

In the "juice fasting" arm, participants will be given vegetable/fruit pressed juices and be instructed to engage in a three-day juice fast diet totaling 800-900 kcal-per-day (nutrient information of juices attached). The specific juices will be assigned for each day in order to maintain the calorie level. In the "juice in addition to normal diet" arm, participants will be given the same juice for three days but continue with their usual diet in addition to the juice. For this

arm, there is no restriction of caloric intake or restriction to liquid only. In the "caloric restriction diet" arm, participants will be on a whole-food plant-based diet totaling 800-900 kcal-per-day (matching the daily calories of juice fasting).

Packaged food and drink will be provided, delivered by the manufacturers (KitchFix and Pressed Vibrance), but participants will need to have access to their own food storage, such as a refrigerator. Deliveries will occur at a place and time of day specified by the participant to ensure delivery to the participant and immediate refrigeration, and both the participant and study coordinator will be notified when deliveries occur. Pressed Vibrance deliveries will be in cooler bags lined with ice packs on all sides, kept roughly 37-39 degrees Fahrenheit. KitchFix deliveries will be in cooler bags with a frozen water bottle, often delivered via refrigerated vehicle.

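### The stated totals of Group 3 menus 2 (879 kcal) and 4 (862 kcal) cannot both agree with the printed item calories, and on the item data menu 2 falls below the 800-900 kcal/day said to match the juice arm

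*Protocol*

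**What the plan says.** The Group 3 section (Caloric Restriction) introduces its tables with "This group will be provided with the meals below to make up their 900 calorie daily diet". The daily meal plan table then lists four menus with totals of 881, 879, 889 and 862 kcal. Two of them share the root-vegetable side:

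- Menu 2: "Herbed Root Vegetable Side + Spice Roasted Sweet Potato Side + Paleo Blueberry Muffin + Broccolini", with the total 879
- Menu 4: "Strawberry Cashew Yogurt + Herbed Root Vegetable Side + Tomato and Roasted Garlic Soup 862"

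The item tables that follow give calories and nutrients for each dish. Under Procedures Involved the protocol says of this arm that "participants will be on a whole-food plant-based diet totaling 800-900 kcal-per-day (matching the daily calories of juice fasting". The juice menu for Group 1 lists six juices, one of each per day.

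**The concern.** The meal plan table defines what Group 3 receives, and it is the only support for the statement that this arm is matched in calories to the juice arm. That match is what lets a comparison of Group 1 with Group 3 separate the effect of juice from the effect of eating less. If a menu total does not follow from its own items, the stated range and the match cannot be relied on for that day. The sign of the difference between arms may also be wrong: the table puts menu 2 at 59 kcal above the juice arm (879 - 820), while the items put it below.

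**Working it through.** **Inputs.** Stated totals from the meal plan table: 881, 879, 889, 862. Item calories from the item tables: mash 75, yogurt 453, quinoa bowl 353, sweet potato 229, muffin 162, broccolini 81, soup 187. The calorie figure of the root-vegetable side is not legible in the text used here, so call it H. Its nutrients are legible: fat 3.7 g, carbohydrate 45.6 g, fiber 10.3 g, protein 4.6 g. Where macronutrients are converted to energy, 9, 4 and 4 kcal per gram of fat, carbohydrate and protein are assumed, with and without fiber.

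**1. The menus without H.**

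- Menu 1: 75 + 453 + 353 = 881, as stated.
- Menu 3: 162 + 75 + 229 + 353 = 819, against 889 stated. It reproduces only if the sweet potato side is 299.
- The sweet potato entry ("Total Carbs (g): 66.1", fat 2.2 g, fiber 10.4 g, protein 5.3 g) gives 2.2×9 + 66.1×4 + 5.3×4 = 305, or 264 net of fiber. So 299 is plausible, and both values are carried below. Menu 3 lies within 800-900 either way.

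**2. Menu 2 minus menu 4.** H cancels.

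- Stated: 879 - 862 = +17.
- Items as printed: (229 + 162 + 81) - (453 + 187) = 472 - 640 = -168. Conflict 185 kcal.
- Items with 299: 542 - 640 = -98. Conflict 115 kcal.

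**3. Could one misread character explain it?** A single wrong digit shifts a figure by d×10^k (d = 1 to 9, k = 0 to 2). To produce 185, one shift must be 5 in the units place, which leaves 180 or 190. Neither is a single-digit shift. At least three digits among the seven figures would have to be wrong.

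**4. Value of H.**

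- Menu 4 requires 862 - 640 = 222.
- Menu 2 requires 879 - 472 = 407, or 879 - 542 = 337 with 299.
- The side's macronutrients give 3.7×9 + 45.6×4 + 4.6×4 = 234, or 193 net of fiber.

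The macronutrients fit 222 and fit neither 407 nor 337. Taking 407 or 337 would put menu 4 at 1047 or 977.

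**5. Size of menu 2.**

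| H | Sweet potato 229 | Sweet potato 299 |
|---|---|---|
| 193 | 665 | 735 |
| 222 | 694 | 764 |
| 234 | 706 | 776 |

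With H, sweet potato and muffin all at their gross macronutrient values and broccolini as printed, menu 2 is 234 + 305 + 177 + 81, about 798. To reach 800, H would have to be 328 (229 case) or 258 (299 case).

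**6. The one item that could rescue the table.** The entry "Broccolini, 226.8 g" appears only in menu 2. With H = 222 and sweet potato 299, all four totals would hold if it were 879 - 222 - 299 - 162 = 196 instead of 81. With fat 0.9 g and protein 6.6 g, 196 kcal needs (196 - 8.1 - 26.4)/4 = 40.4 g of carbohydrate, against 11.6 g for 81 kcal. The item shows 6.1 g fiber and 3.9 g sugars.

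**7. Against the juice arm.** 140 + 170 + 120 + 130 + 120 + 140 = 820. Menu 2 is 126 kcal below that (694) or 56 below (764).

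**8. Three-day means, H = 222.** The protocol does not say which three of the four menus are used.

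| Menus | Stated | With 299 | With 229 |
|---|---|---|---|
| 1, 2, 3 | 883 | 845 | 798 |
| 1, 2, 4 | 874 | 836 | 812 |
| 2, 3, 4 | 877 | 838 | 792 |
| 1, 3, 4 | 877 | 877 | 854 |

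**The case against.** The contradiction itself has no answer in the protocol. The case on the other side concerns its consequence and its size.

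- **The three-day match does not get worse.** Samples are taken before and after the whole intervention, so intake over three days is what bears on the endpoints. In every set that contains menu 2, the stated mean is 54-63 kcal above 820, while the recomputed mean is 16-25 above (with 299) or 8-28 below (with 229). This stands, and it limits the harm. It does not make the 879 correct, and with 229 two of the four possible means fall under 800.
- **The larger figures may rest on a misread digit.** The item tables are damaged in extraction, and 299 fits menu 3 and the item's macronutrients where 229 fits neither. This too has weight: 115 kcal and 764 kcal are the safer figures, and 185 and 694 apply only if 229 is what the protocol prints.
- **Menu 2 being below 800 is inferred.** It needs H, taken from menu 4 and from macronutrients, and at the gross-macronutrient extreme the margin is only about 2 kcal. An error in the broccolini figure cannot be fully excluded, because its carbohydrate value is cut off here. But if broccolini were 196, its printed 81 would be wrong and the table would still need correcting.
- **Exposure is uncertain.** Four menus are listed for three days, so menu 2 may not be used by everyone. The 820 comparator assumes one of each juice daily, as the Group 1 section says; Procedures Involved speaks of specific juices assigned by day.

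**Conclusion.** The concern holds. Menus 2 and 4 cannot both have their stated totals on the printed item calories. They conflict by 185 kcal as printed, or by 115 kcal if the sweet potato side is 299, and neither figure depends on the illegible root-vegetable value. Confidence in this part is high.

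The protocol's own item data place the discrepancy in menu 2. It comes to 764 kcal (13% below the stated 879, 36 below the 800 floor) with 299, or 694 kcal (21% and 106) with 229. This part is an inference. It assumes H of about 222, supported by menu 4's total and by macronutrients at 9/4/4 kcal per gram, and it takes broccolini at its printed 81.

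The effect on a three-day average is modest. The point should be fixed because the table specifies the intervention and underpins the matching statement, but it does not by itself undermine the comparison between arms.

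**What to change.** Before meals are ordered, check against the vendor labels the item calories (in particular the root-vegetable, sweet potato and broccolini entries), the four menu totals, the 900-calorie statement in the Group 3 section, and the 800-900 kcal matching statement under Procedures Involved. Then make these passages agree and print the corrected daily totals for Groups 1 and 3. Which figure is right is for the sponsor to determine.

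The cost is one check of labels and a corrected table. It needs no extra participants, visits or assays.

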In all three arms, the three-day diet intervention will be preceded and followed by three days of self-conducted elimination diet. The pre-intervention diet will encourage participants to eat a healthy, light diet for three days (basic instructions: eat only fresh raw or cooked fruits and vegetables (preferably organic), whole grains and eggs; drink 8 glasses of water a day; avoid or eliminate alcohol, caffeine, sugar, processed foods, dairy, red meat, and gluten). The post-intervention diet will instruct participants to gradually return to eating solid foods, and limit strenuous exercise (basic instructions: follow a diet similar to the pre-intervention elimination diet; day 1 after the intervention: eat fruits & green vegetables, and drink 8 glasses of water; day 2 add in: nuts, gluten-free grains like whole oats, quinoa, or brown rice; day 3 add in: organic meats, fish, & gluten-containing grains).

Biological samples and self-reported outcomes will be collected at four time points: baseline (prior to the first elimination diet period), pre-intervention (after the elimination diet and before the three-day intervention), post-intervention (after the intervention), and 14-day post-intervention. At each time point, participants will complete questionnaire on quality of life (PROMIS - Global Health Scale, which is an NIH measure on an individual's' overall physical and psychological well-being; see appendix) and collect their own saliva and stool samples. Participants will be given self-administered toolkits and be taught how to collect the samples at their first lab visit. At each of the four time points, the research assistant will coordinate the collection of cheek swabs and bloodspot samples. Stool samples will be collected using a premoistened wipe, with written instructions provided to participants, and both stool and saliva samples will be collected by the participant at home, then provided to the research assistant at their next visit.

Over the course of the study, participants will be instructed to keep a diet diary days one through nine to record their dietary intake of each day (diet diary forms with instructions attached), as well as fill out a modified version of the PROMIS Global Health Scale. During the intervention period, the research team will also contact the participants to check in with them. Participants will not need to record diet data for the fourteen day post intervention period.

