This study will not include vulnerable populations (adults unable to consent, individuals who are not yet adults, pregnant women, and prisoners).

PARTICIPANT POPULATIONS:

Number:	Category/Group:	Consented:	Enrolled:
	Special/Vulnerable	Consented or Reviewed/Collected/Screened	Number to Complete the Study or Needed to Address the Research Question
Local	Adults	30	18
Study-wide	N/A	N/A	N/A
Total:		30	18

RECRUITMENT METHODS:

Flyers will be posted on the Evanston campus of Northwestern University. Interested individuals will be directed to complete a screening questionnaire online via REDCap which will include questions about general health conditions (from SF-36) and demographics. Based on the inclusion and exclusion criteria, qualified individuals would be contacted for a phone call to gauge their interest in participating in the study. This data will not be used in the study – it will be solely for the purposes of determining eligibility, and will be housed in a separate REDCap database. During the phone conversation, detailed information will be given on what participating in the study entails, and participants will be asked at the end whether they are willing to participate. If the answer is yes, they will be invited for the initial lab visit during which hard-copy consent form will be provided.

COMPENSATION FOR PARTICIPATION IN RESEARCH ACTIVITIES

Participants will be compensated for their participation in the study. Each participant will be given a gift card for \$50 when they complete the third collection of biological samples and surveys, and \$50 when they complete the final collection of biological samples and surveys.

WITHDRAWAL OF PARTICIPANTS:

Participants will have the opportunity to voluntarily withdraw throughout the study. Involuntary withdrawals will be initiated when participants report experiencing an adverse medical event (e.g., fainting or other health effects that may be related to fasting and caloric Version #:1.4 Version Date: 05/22/2018

STU#:00206611 restriction).

Failure to collect samples for one or more time periods will be reviewed on a case-bycase basis.

RISKS TO PARTICIPANTS:

Risks to participants are expected to be minimal, particularly in light of the valuable information to be gained.

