Diet intervention: Fasting and juice cleanse diets over short periods are generally safe, but may cause some minor discomfort during the study period. For those on restricted intake diets, several minor adverse effects may occur and include constipation, headache, muscle cramps, diarrhea, general weakness, and rash. Most of these are short-lived, and are generally alleviated by adequate fluid intake and other minor diet modifications. The restricted diet may lead to decreases in glucose levels; this risk will be mitigated by screening participants for the exclusion criteria of diabetes, hypoglycemia, steroid-dependent diseases and use of medications that impact on blood sugar such as sulfonylureas and insulin.

Blood Spot: There is a small risk that the puncture associated with the blood spot may cause bruising or infection at the site of the needle insertion.

Weight, height and waist circumference measurements: There is no physical risk involved in measuring weight, height, and waist circumference but there is a risk of embarrassment or discomfort at being measured in one's underclothes.

Behavioral and psychological questionnaires: These carry a minimal risk for emotional discomfort and stress.

Participants will be fully informed of all of these risks during the informed consent process and be given the opportunity to withdraw from the study at any time without any further obligation. No data will be collected until informed consent has been obtained. We expect all of these risks to be temporary, and to quickly subside after the study is concluded.

Efforts to minimize risk are as follows:

Dietary intervention: Participants will be instructed to speak to the research associate or principal investigator if they experience discomfort, such as constipation, diarrhea, weakness, muscle cramps, or dizziness. There is instruction provided with the juice cleanse on how to address any potential side effects stemming from the diet. Participants will be told that their participation is voluntary and they can choose to withdraw from the study at any time without any further obligation.

Blood spot: Bloodspot collection will be done as professionally and comfortably as possible. Blood is collected for the in-person assessments in a sterile manner to reduce the threat of infection. Likewise, pressure is applied to the puncture site to prevent hemorrhage and ecchymosis.

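### Participants are told their arm at the initial visit, so the self-conducted run-in and every pre-intervention sample follow disclosure, although the run-in is the same in all arms

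*Protocol*

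**What the plan says.** Under Procedures Involved, participants attend an initial lab visit, complete questionnaires on usual diet and demographics, and "will be informed about their assignment to one of the three arms". Consent belongs to the same visit: under Recruitment Methods, people who agree by telephone are told that "they will be invited for the initial lab visit during which hard-copy consent form will be provided". Risks to Participants adds: "No data will be collected until informed consent has been obtained".

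On stool and saliva, Procedures Involved states: "Participants will be given self-administered toolkits and be taught how to collect the samples at their first lab visit". It adds that "both stool and saliva samples will be collected by the participant at home, then provided to the research assistant at their next visit". Cheek swabs and bloodspots are coordinated by the research assistant at each of the four time points, and PROMIS is completed at each of them.

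In all three arms the intervention is "preceded and followed by three days of self-conducted elimination diet". Baseline is defined as before the first of these diets, and pre-intervention as after it and before the intervention. Study Endpoints defines the primary endpoints as changes in epigenetic markers, gut microbiota, and markers of inflammation and insulin resistance. No section withholds the arm from the participant until any sample has been taken.

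**The concern.** A primary endpoint defined as a change is only as sound as its reference value. If the reference is taken after participants know their arm, and after three days of unsupervised eating that this knowledge can influence, the reference may differ between arms for reasons unrelated to the intervention.

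The arms differ sharply in burden: two allow 800 to 900 kcal a day, while the third adds juice to an unrestricted usual diet. A person who expects a fast may prepare more carefully or eat more beforehand; a person who expects usual food may treat the run-in lightly. The run-in limits alcohol, caffeine, sugar, processed food, dairy, red meat and gluten, exposures that could plausibly move the microbiota and glycemic markers.

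Knowledge of the arm also lets someone leave before the intervention because they dislike their allocation. That loss comes after randomisation and is related to the arm. Later analysis cannot recover a reference taken before disclosure if none was collected.

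**Working it through.** **Order of events**

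1. Consent is given at the initial visit and no data precede consent, so no study sample precedes that visit.
2. The arm is disclosed and the collection kits are handed out at that visit.
3. Baseline stool and saliva are collected at home and returned at the following visit, so they come after disclosure.
4. The three-day run-in follows baseline, so it comes after disclosure.
5. Pre-intervention stool, saliva, bloodspot, cheek swab and PROMIS follow the run-in, so all come after disclosure.
6. Baseline bloodspot, cheek swab and PROMIS may be taken at the initial visit. Their order relative to disclosure is not stated.

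For stool and saliva, therefore, neither possible reference is taken before disclosure. For blood, cheek swab and PROMIS, the pre-intervention reference is not, and the baseline reference is undetermined.

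**Expected loss**

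Participant Populations gives 30 consented and 18 to complete. Procedures Involved expects six per arm after attrition, and 3 × 6 = 18. The loss is 30 − 18 = 12, or 12/30 = 40%; in reverse, 18/(1 − 0.40) = 30. The figure of 36 under Qualifications reproduces as 18/(1 − 0.50); its 50% also counts ineligible people, so it does not conflict with the 40%.

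If allocation is equal (the ratio is not stated), each arm starts with 10. Illustrative splits of the 12 losses, all assumed:

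| Losses by arm | Completers by arm |
|---|---|
| 4 / 4 / 4 | 6 / 6 / 6 |
| 6 / 2 / 4 | 4 / 8 / 6 |
| 7 / 2 / 3 | 3 / 8 / 7 |

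The Protocol does not say how many losses would fall in the run-in.

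**Bias in a change score**

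Let *s* be the full effect of the run-in on a marker (in SD), *g* the adherence gap between two arms, and *c* the share of the run-in effect still present at the post-intervention sample. The pre-intervention values then differ by *s × g*, and the pre-to-post contrast is biased in absolute size by *s × g × (1 − c)*.

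None of the three inputs is in the Protocol. With *s* = 0.5 SD and *g* = 0.4 as assumptions:

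- no carry-over (*c* = 0): 0.5 × 0.4 × 1 = 0.2 SD (0.1 SD at *g* = 0.2; 0.3 SD at *g* = 0.6);
- full carry-over (*c* = 1): 0.5 × 0.4 × 0 = 0.

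The 0.2 SD is thus the upper end for those inputs. If the change is measured from baseline instead, the same adherence gap enters through the post-intervention value, as *s × g × c*.

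For scale, with six per arm the standard error of a difference between two arm means is √(2/6) = 0.58 SD, in SDs of the measure analysed.

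**The case against.** The strongest reply has four parts.

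**The baseline sample.** It is taken on the usual diet, before the run-in, so different run-in adherence cannot reach it. This stands. All that remains for baseline stool and saliva is behaviour between disclosure and collection, a lesser matter. A reader might infer that every baseline sample is compromised. The Protocol does not support that: the inflammatory and glycemic markers and the genome-wide methylation assay come from blood, and baseline blood may be drawn before the arm is disclosed.

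**The size.** Any figure in SD rests on assumed inputs and may shrink to nothing with carry-over. The illustrative 0.2 SD is about a third of the 0.58 SD standard error (0.2/0.58 = 0.34). This stands too. However, such a bias would be systematic, and one aim is to lay a foundation for larger studies, where more participants would not remove it. Which time point serves as reference, and whether the analysis adjusts for it, may be settled in an analysis plan not seen here. Adjusting for a reference already influenced by the arm would not restore an unaffected one.

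**Existing safeguards.** Diet diaries for days one to nine appear to cover the run-in. Eligibility excludes people unlikely or unable to change their diet. Participation is explained by telephone before the visit, and the first payment comes only at the third collection. These reduce the concern without removing it: diaries record adherence but do not equalise it, and the telephone call cannot reveal which arm a person will get. Daily contact is specified for the intervention days; the adherence calls under Qualifications do not say whether they include the run-in.

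**Masking.** These diets cannot be masked once begun, and arm-related loss during and after the intervention would remain whenever the arm is disclosed. True, but the run-in is the part where masking is possible, because its instructions do not differ by arm.

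**Conclusion.** The point holds in limited form. The stated order puts the run-in, all pre-intervention samples and questionnaires, and home-collected baseline stool and saliva after disclosure, and nothing in the run-in requires it. The main exposure is the pre-intervention reference for the primary change endpoints; arm-related loss in the run-in comes second; baseline stool and saliva come last.

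The only firm figure is the planned loss of 12 of 30. The share falling in the run-in and the size of any bias cannot be derived from the Protocol.

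A reader might go further and infer that the randomisation is invalid or that the contrasts are known to be biased. Neither follows. The Protocol shows that references and drop-out can depend on the arm, not that they will. This is an avoidable weakness worth correcting, not a contradiction or a miscalculation.

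**What to change.** In Procedures Involved, separate allocation from disclosure:

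- Generate the allocation early enough for staff to place the food order, but conceal it from the participant until the pre-intervention samples and questionnaires have been collected. Moving randomisation itself to the pre-intervention visit would be awkward, because staff must know beforehand which supplier to use.
- At the first visit, take the delivery place and time for later use; the participant can give these without knowing the arm.
- Schedule deliveries after disclosure. Participants are notified of deliveries, and juices and meals come from different suppliers, so an early delivery or notice would reveal much of the allocation.
- Report losses before and after disclosure by arm.

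If full concealment through the run-in proves unworkable, disclosing only after baseline stool and saliva are returned would protect the baseline reference, but not the run-in or the pre-intervention one.

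The change alters no diet. It costs a wording change, tighter scheduling between the pre-intervention collection and the first intervention day, and an occasional wasted order when someone leaves during the run-in.
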